Each group will receive a single dose of live JE vaccine IMOJEV®. All doses will be administered at the LUHFT CRU facility in accordance with a bespoke vaccination administration working instruction. Group 1 participants will be in the study for 28 days and will give 6 blood samples, one on the day vaccination and then daily on days 5 through to 9 post vaccination. Group 2 and 3 participants will be in the study for a total of 8 weeks and will be expected to attend study visits and provide six blood samples at baseline, and weeks 1, 2, 4, and 8 (see Figure 2, Study Schedule). All participants will have Adverse Events (AEs) recorded while they are in the study. Sample collection in the Acute emerging Virus Immunity study (AVIS) will be temporarily suspended during FlaviPrime, participants will then revert back to AVIS once the FlaviPrime sampling collection period has finished. Participants will be followed up, aiming for 5 years of follow up, and have already been consented for storage of contact details for future studies.

5.1 Blinding

This is an open label study with no blinding requirements. All researchers and participants know which treatment / intervention is being administered.

5.2 Study Setting

Participants will be identified and recruited from an existing observational study (“Immune responses to Zika virus and other flaviviruses,” (Acute emerging Virus Immunity Study, AVIS) 16/NW/0170), by advertisement, and through Liverpool University Hospitals NHS Foundation Trust (LUHFT) Clinical Research Unit (CRU), for example using the consent4consent database. Follow up will occur at LUHFT.

5.2.1 Selection of Participating Sites

FlaviPrime is a single centre study that will undertake intensive laboratory investigation of the immune response to IMOJEV®. Therefore, the study site must be close to the necessary facilities (single cell sorting, sequencing, etc.) and will only be open at one site, the LUHFT CRU, which has the necessary expertise for this study.

The site will be opened to recruitment upon successful completion of all global (e.g. REC) and study-specific conditions (e.g. site personnel training requirements) and once all necessary documents have been returned to the CTU. Initiation of the site will be undertaken in compliance with LCTC internal processes. Conditions and documentation required will be detailed on a LCTC Green Light Checklist maintained in the TMF and must be fully completed prior to opening sites to recruitment.

5.2.2 Selection of Principal Investigators

Principal Investigators will be required to demonstrate equipoise, relevant experience and commitment during early stage feasibility assessment. All investigators will have the particular medical expertise necessary to conduct the study in accordance to the protocol and all regulatory and ethical requirements. Written agreement to conduct research as such will be obtained prior to site initiation.

A suitable co-investigator should be identified at each site to deputise in case of PI absence.

6 ELIGIBILITY CRITERIA

The FlaviPrime study aims to recruit up to 25 participants based on sample size calculations described in Section 12.2. All patients must provide written, informed consent before any study procedures occur (see Section 9.2 for more information regarding informed consent processes) and must meet all eligibility criteria as described below.

6.1 Inclusion Criteria

Patients eligible for the study must comply with all of the following at registration:

1. A male or female adult between 18 and 70 years of age at consent.
2. Written and informed consent obtained from participant and agreement of participant to comply with the requirements of the study
3. Able to attend regularly to donate study blood samples for the duration of the study (8 weeks), no planned re-location or travel to a flavivirus endemic area during the study period.
4. Satisfactory medical screen, as demonstrated by study screening document normal physical examination and normal screening blood tests
5. Group 1: Any flavivirus exposure status; Group 2: No previous flavivirus vaccination (JE, tick borne encephalitis or yellow fever (YF)), no residence in a flavivirus endemic area nor planned travel to a flavivirus endemic area during the period of the study; Group 3: JE vaccine and/or yellow fever vaccine or other proven flavivirus infection within the last 10 years or other proven flavivirus infection (lifetime).
6. An efficacious method of contraception must be used during the study for 28 days after vaccination for women of childbearing potential (see section 11).

6.2 Exclusion Criteria

Any patient meeting any of the criteria listed below at baseline will be excluded from study registration:

1. Use of any investigational or non-registered drug within 5 half-lives of the drug, or 30 days preceding administration of study JE vaccine, whichever is longer; or planned use during the study period.
2. Receipt of any investigational biologic agents with mechanisms of action that might affect the immune system, at the discretion of the CI and local PI.
3. Administration of immunosuppressants or other immune-modifying drugs within a period of six months before vaccination or at any time during the study period; participants who have received these agents may also be excluded at the discretion of the CI and local PI.
4. Any confirmed or suspected immunosuppressive or immunodeficient condition.
5. A family history of congenital or hereditary immunodeficiency.
6. Any antiviral drug therapy within a period of 5 drug half-lives or 30 days before vaccination, whichever is longer, or at any time during the study period.
7. History of significant allergic reactions likely to be exacerbated by any component of the study vaccine, especially allergic disease or reactions to any previous dose of any vaccine.
8. History of having received JE vaccine, yellow fever vaccine, tick-borne encephalitis vaccine or experimental flavivirus vaccine (group 2 only).

9. Acute disease (for example acute infection) at the time of enrolment or vaccination, if symptoms are rated as anything more significant than a mild adverse event. Entry into the study and/or vaccination may be deferred until the illness has resolved for at least one week.
10. Acute or chronic, clinically significant in the opinion of the investigator, disease in any organ system, as determined by history, physical examination or laboratory testing.
11. Presence of any inflammatory condition that might require immunomodulatory therapy.
12. Recent blood donation (inclusion can be delayed under these circumstances; the participant should be enrolled 16 weeks after their last blood donation. Each participant should give no more than 470 ml per 16 weeks, so regular blood donation should be suspended during the study and can re-commence 1 month after the last study sample).
13. Current or previous abattoir worker or sheep farmer in Scotland (risk of Louping ill virus exposure; group 2 only).
14. Administration of immunoglobulins and/or any blood products within the three months preceding administration of vaccine, or planned administration during the study period.
15. Seropositive for HIV.
16. Pregnancy or Lactation.
17. History of excessive alcohol consumption (>28 units per week), drug abuse or significant psychiatric illness.
18. Any other condition or consideration that, in the opinion of the Investigator, would pose a health risk to the participant if they were enrolled in the study, or would otherwise interfere with the evaluation of the study aims (e.g. difficult venesection).

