	
2. Receipt of any investigational biologic agents with mechanisms of action that might affect the immune system, at the discretion of the CI and local PI.3. Administration of immunosuppressants or other immune-modifying drugs within a period of six months before vaccination or at any time during the study period; participants who have received these agents may also be excluded at the discretion of the CI and local PI.4. Any confirmed or suspected immunosuppressive or immunodeficient condition.5. A family history of congenital or hereditary immunodeficiency.6. Any antiviral drug therapy within a period of 5 drug half-lives or 30 days before vaccination, whichever is longer, or at any time during the study period.7. History of significant allergic reactions likely to be exacerbated by any component of the study vaccine, especially allergic disease or reactions to any previous dose of any vaccine.8. History of having received JE vaccine, yellow fever vaccine, tick-borne encephalitis vaccine or experimental flavivirus vaccine (group 2 only).9. Acute disease (for example acute infection) at the time of enrolment or vaccination, if symptoms are rated as anything more significant than a mild adverse event. Entry into the study and/or vaccination may be deferred until the illness has resolved for at least one week.10. Acute or chronic, clinically significant in the opinion of the investigator, disease in any organ system, as determined by history, physical examination or laboratory testing.11. Presence of any inflammatory condition that might require immunomodulatory therapy.12. Recent blood donation (inclusion can be delayed under these circumstances; the participant should be enrolled 16 weeks after their last blood donation. Each participant should give no more than 470 ml per 16 weeks, so regular blood donation should be suspended during the study and can re-commence 1 month after the last study sample).
--	---

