6.3 Co-enrolment Guidelines

Participants can enter FlaviPrime if they are participating in other studies, provided that: i) no experimental drug is taken five half lives before the screening and for the 8 week period after vaccination, ii) no experimental vaccine is given within 4 weeks before screening or after vaccination in this study, and iii) the total volume of blood drawn in a 16-week period does not exceed 470 ml (the same volume as would routinely be collected during blood donation). Participants will remain in the Acute and emerging Virus Immunity Study (AVIS). Enrolment into any new study should take place >8 weeks after vaccination in FlaviPrime, unless there is a pressing reason for enrolment, and the discretion of the chief investigator. In any event, the FlaviPrime study team should be informed of any new enrolment into a study during the 28 period (group 1) or 8 week period (groups 2 and 3) following vaccination.

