Medication	Not to take medication that will impair or alter their immune response, for example; 
 - Corticosteroids, including inhaled steroids - Colchicine - Azathioprine, other cell cycle inhibitors or chemotherapy agents - Methotrexate or other anti-metabolites - Any biologic immunosuppressive or immunomodulatory drug, - Insulin or other oral anti-diabetic drug - Any vaccine other than that being given as part of the study (COVID vaccines can be given) 	To ensure the response seen is due to the body, and not other medication. If it is necessary to take certain medications for participant health, participants will be asked to inform the study team as soon as they can.
Travel	Not to travel to any country where Flaviviruses are found from screening till 8 weeks after the vaccination	To limit exposure to a flavivirus which could create another response
Alcohol	Not to drink more than 28 units of alcohol a week e.g. 
 - 16 bottles of larger, beer or cider - 2 and half bottles of wine 	Alcohol may affect the body's response to the vaccine
Other studies	Not to take part in other studies until 8 weeks after receiving IMOJEV®	To ensure the response we see is due to IMOJEV® and not another study
Blood donation	Not to donate blood for 3 months after vaccination	There is a limit to the amount of blood a person can give in a 3 month period
Contraception	Female partners of childbearing potential of male participants in the study must use an acceptable method of contraception from the time of screening until 28 days after vaccination. Females of childbearing potential must use an acceptable method of contraception from the time of screening until 28 days after vaccination.	IMOJEV® is not suitable for use in pregnant women

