9.6 Sampling

Sample Collection

The blood volumes that will be taken from each participant are detailed in the schedule of study assessments. The maximum blood volume to be taken per participant will be approximately 300ml, or 330ml for group 1, which is less than the volume of a single blood donation.

People who are blood donors can participate in FlaviPrime, but they cannot give blood concomitantly to the study. The maximum amount of blood that can be given in blood donation is 470 ml per 16 weeks. Therefore, a participant who is a blood donor cannot join FlaviPrime until 16 weeks after their last blood donation. Four weeks after the last FlaviPrime study sample is taken, the participant becomes is able to donate blood again.

Sample Shipment/Custodianship

Laboratory safety samples will be analysed at the Royal Liverpool University Hospital Laboratories. Experimental blood samples relating to the outcomes of this study will be analysed within the Department of Clinical Infection, Microbiology and Immunology, University of Liverpool. Samples will be transported from the CRU to the University of Liverpool in line with the study specific Material Transfer Agreement (MTA). Details of sample transport are in the bespoke laboratory manual for the study. Serological analyses will be performed in the laboratory of [name], Mahidol University, and Bangkok. Depending upon the initial results of the study, it may be beneficial to send samples to other laboratories, as is the case in the Acute emerging Virus Immunity Study.

Sample Storage and Handling

Samples given as part of the study, if they are not used in meeting the scientific objectives, will be stored for a period of 25 years. The samples can be used in future studies addressing the development of immunity to flaviviruses, and the cross-reactivity to flaviviruses, and to other emergent viruses, but not for other purposes (control antigens/mitogens will also be included). An example of such a use might be, testing for markers of immunity to a flavivirus or another virus that is undiscovered at the time of the study, but causes an outbreak in the future.

These samples would be used for the purposes as outlined above in section 7.3.1, although these may apply to other viruses. Permission to send material to other laboratories, and the parameters of the purpose of this, will be included in the consent form at the start of the study.

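### No stated date for resuming blood donation keeps a participant within the protocol's cap of 470 ml per 16 weeks, and for group 1 the dates differ by about seven weeks

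*Protocol*

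**What the plan says.** **The cap.** Criterion 12 reads the same in section 2 and section 6.2: "Each participant should give no more than 470 ml per 16 weeks". Section 6.3 allows co-enrolment only if "the total volume of blood drawn in a 16-week period does not exceed 470 ml", and adds that this is the volume of one routine donation.

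**When donation may resume.** Three rules are given:
- Criterion 12 draws its rule from the cap: donation stops while the participant is in the study and "can re-commence 1 month after the last study sample".
- Section 9.6 gives four weeks after the last study sample.
- The restrictions table in section 7.7 says "Not to donate blood for 3 months after vaccination", with the reason that "There is a limit to the amount of blood a person can give in a 3 month period".

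**Study blood.** Section 5 states that "Group 1 participants will be in the study for 28 days and will give 6 blood samples", on the day of vaccination and on days 5 to 9. Groups 2 and 3 are sampled at baseline and at weeks 1, 2, 4 and 8, the last visit being day 56 with a 7-day tolerance either way. Section 9.6 gives the totals: "The maximum blood volume to be taken per participant will be approximately 300ml, or 330ml for group 1".

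**Before entry.** Sections 6.2 and 9.6 make a donor wait 16 weeks after the last donation before joining.

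**The concern.** Criterion 12 presents the resumption date as a consequence of the cap, but it does not follow from it. The cap equals one donation, so any study blood from the previous 16 weeks puts a donor over the limit. The 16-week interval is applied to donations before the study and dropped, without explanation, for donations after it.

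The three rules also use different starting points (last sample or vaccination), and section 7.7 describes the limit per three months instead of per 16 weeks. Group 1 has its last draw on day 9, so the rules diverge widely there.

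At stake is a participant-protection limit: staff cannot apply it consistently, and a donor who keeps to any of the stated dates can still exceed it.

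**Working it through.** **Inputs**
- Tube volumes (section 9.5 schedule): 3.7 + 2.5 + 8.5 + 40 = 54.7 ml per visit. In groups 2 and 3 the week 1 heparin volume is 60 ml instead of 40 ml, which adds 20 ml.
- Cap: 470 ml in 16 weeks, that is 112 days. One routine donation: 470 ml (section 6.3).
- Vaccination is day 0. I take one month as 28–31 days and three months as about 91 days.

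**Reproducing the stated study volumes**
- Group 1: 6 × 54.7 = 328.2 ml (stated: about 330 ml).
- Groups 2 and 3: 5 × 54.7 + 20 = 293.5 ml (stated: about 300 ml).

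Both agree, and both are below 470 ml. Screening tubes have no stated volume, and section 5 speaks of six samples for groups 2 and 3 while listing five time points, so these totals are lower bounds.

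**Resumption dates**

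| Rule | Group 1 (last sample day 9) | Groups 2 and 3 (last sample day 56) |
|---|---|---|
| Sections 2, 6.2, 9.6 | 9 + 28 = 37 to 9 + 31 = 40 | 56 + 28 = 84 to 56 + 31 = 87 |
| Section 7.7 | about 91 | about 91 |
| Difference | 51–54 days | 4–7 days |

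With the visit tolerance (last sample on day 49–63), the dates for groups 2 and 3 under sections 2, 6.2 and 9.6 run from 49 + 28 = 77 to 63 + 31 = 94. Day 94 is the latest date under any rule. It is before day 112, so even the baseline sample still counts.

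**Blood in the 16 weeks ending with a donation on any stated date**
- Group 1: 328.2 + 470 = 798.2 ml; 798.2 / 470 = 1.70.
- Groups 2 and 3: 293.5 + 470 = 763.5 ml; 763.5 / 470 = 1.62.

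**Section 7.7 on its own three-month window.** That section gives no volume, so I assume the same 470 ml. At day 91 only the baseline draw has dropped out.
- Group 1: 328.2 − 54.7 + 470 = 743.5 ml.
- Groups 2 and 3: 293.5 − 54.7 + 470 = 708.8 ml.

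**Earliest date that complies.** The last sample alone plus one donation is 54.7 + 470 = 524.7 ml, already over the cap. A full donation therefore has to wait 16 weeks from the last sample:
- Group 1: 9 + 112 = day 121.
- Groups 2 and 3: 56 + 112 = day 168 (161–175 across the visit tolerance).

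**The case against.** The strongest reply is that the cap limits donations only. Section 9.6 words it that way in one sentence and then allows donation four weeks after the last sample. The total-volume wording in section 6.3 belongs to co-enrolment. Read literally as a rolling total, the cap would let a single 54.7 ml draw bar donation for 16 weeks, and the authors may not have meant that, since they put the one-month date in the same sentence as the cap.

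This does not carry. Section 9.6 itself uses the limit to keep a donor out of the study for 16 weeks. Section 7.7 bars donation after vaccination because of a limit on blood given. Criterion 12 suspends donation during the study because of the cap. Each of these makes sense only if study blood and donations are added together.

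Three points do stand:
- The overshoot needs a voluntary full donation after the visits; no study procedure breaches the cap.
- The section 7.7 table is the participant-facing restriction. The amendment log says it was already in the participant information and ties no other date to that document, so conflicting advice to participants is not shown.
- The conflict between dates matters mainly for group 1, which has 3–4 people.

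It is also fair to say that a 16-week wait after a small last draw is strict. It nevertheless follows from the cap as written.

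**Conclusion.** The concern holds. Every stated resumption date permits a donation that exceeds the cap: by 70% in group 1 and 62% in groups 2 and 3, assuming a routine 470 ml donation and study blood counted with donations. The breach itself does not depend on exact tube volumes, on the length taken for a month, or on the visit tolerance, because one donation already equals the cap.

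The group 1 disagreement of 51–54 days, with three months taken as 91 days, holds on any reading of the cap. For groups 2 and 3 the nominal gap is under a week or about a week.

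The weight is minor. It concerns only voluntary donors among at most 25 participants and has no bearing on the analysis.

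**What to change.** State one rule in criterion 12 (sections 2 and 6.2), in sections 7.7 and 9.6, and in the participant information: no blood donation until 16 weeks after the last study sample, which is about day 121 for group 1 and about day 168 for groups 2 and 3. In section 7.7, replace the three-month rationale with the cap of 470 ml per 16 weeks.

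The cost is one sentence in each of the four protocol sections and in the participant information. Compared with the day-91 date, a regular donor waits 121 − 91 = 30 days longer in group 1 and 168 − 91 = 77 days (11 weeks) longer in groups 2 and 3.

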6.3 Co-enrolment Guidelines

Participants can enter FlaviPrime if they are participating in other studies, provided that: i) no experimental drug is taken five half lives before the screening and for the 8 week period after vaccination, ii) no experimental vaccine is given within 4 weeks before screening or after vaccination in this study, and iii) the total volume of blood drawn in a 16-week period does not exceed 470 ml (the same volume as would routinely be collected during blood donation). Participants will remain in the Acute and emerging Virus Immunity Study (AVIS). Enrolment into any new study should take place >8 weeks after vaccination in FlaviPrime, unless there is a pressing reason for enrolment, and the discretion of the chief investigator. In any event, the FlaviPrime study team should be informed of any new enrolment into a study during the 28 period (group 1) or 8 week period (groups 2 and 3) following vaccination.

7 STUDY TREATMENT/INTERVENTIONS

7.1 Introduction

Eligible patients in each group will receive a single dose of live, attenuated, JE vaccine IMOJEV®. IMP will be supplied by Sanofi Pasteur in accordance with all applicable guidelines.

7.2 Treatment Name / Description

7.2.1 Live attenuated JE vaccine IMOJEV®

Information on live attenuated JE vaccine IMOJEV® will be available to the investigators in the form of the Investigators Brochure (IB).

The vaccine is a live attenuated virus. Following administration, the virus replicates locally and elicits neutralising antibodies and cell-mediated immune responses that are specific to the Japanese encephalitis (JE) virus. Available results indicate that protection is mainly mediated by neutralising antibodies.

IMOJEV® is a monovalent, live attenuated viral vaccine. The virus was obtained via recombinant DNA technology. It is based on the 17D-204 yellow fever vaccine virus in which two genes have been replaced by the corresponding genes from Japanese encephalitis (JE) virus. These are the premembrane (prM) and envelope (E) coding sequences of the SA14-14-2 live attenuated JE vaccine virus. The immunising antigens are the prM and E proteins from the SA14-14-2 vaccine virus.

Brand name / Active ingredient: IMOJEV®

After reconstitution the active ingredients are:

Live, attenuated, recombinant Japanese encephalitis virus: 4.0 - 5.8 log¹⁰ Plaque Forming Units, Propagated in Vero cells.

Excipients to the above active ingredients are:

- Mannitol
- Lactose
- Glutamic acid
- Potassium hydroxide
- Histidine
- Human Serum Albumin
- Sodium chloride
- Water for injections

No adjuvant or antimicrobial preservative is added.

Formulation:

Powder for reconstitution / diluent

The powder is a white to creamy white homogeneous cake which might be retracted from the sides of the vial. The diluent is a clear solution. After reconstitution, IMOJEV® is a colourless to amber suspension.

Manufacturer:

Sanofi Pasteur

Packaging, storage and stability:

IMOJEV® is provided in separate packs, each pack contains:

- One vial containing a white to creamy white vaccine powder
- One vial (type I glass) each with a stopper (halo-butyl) and a flip off cap (aluminium/polypropylene) containing clear diluent
- One disposable syringe (polypropylene) with 2 separate needles (stainless steel)

The vaccine boxes are to be stored in a refrigerator (2°C – 8°C) not be frozen.

When out of the fridge the vials should be kept in the outer carton in order to protect from light. Do not use IMOJEV® after the expiry date which is stated on the carton after EXP.

Supplier's name:

Sanofi Pasteur

Regulatory Status:

Licensed in Australia and New Zealand for the prevention of JE in travellers.

It is also marketed in some parts of Southeast Asia.

